## 9. STATISTICAL CONSIDERATIONS AND DATA ANALYSES

### 9.1. Hypotheses

The primary objective of the study is to investigate the safety and tolerability of GSK2982772 following 12 weeks of treatment. No formal statistical hypotheses will be conducted to assess this objective.

If appropriate, comparisons between the GSK2982772 and the placebo arm will be made to investigate the secondary pharmacodynamic, mechanistic and efficacy objectives.

Trends over time will be investigated for both treatment arms along with associations between each of the pharmacodynamic, mechanistic and efficacy parameters.

### 9.2. Sample Size Considerations

[figure not shown]
#### 9.2.1. Sample Size Assumptions

The study is not powered to detect pre-defined differences. A sufficient number of subjects will be screened so that approximately 24 subjects with moderate to severe RA are randomised into the study on a TID regimen. Prior to protocol amendment 3 being approved in each country, no more than 18 subjects will be randomised into the study on a BID regimen. [Table 4](#) summarises the total planned sample sizes for BID and TID regimens. Should the drop-out rate be higher than anticipated, additional or replacement subjects may be randomised (up to an overall total maximum of 48) into the study at the discretion of the Sponsor.

**Table 4 Summary of Total Sample Size by Dosing Regimen**

Number Randomised to GSK2982772 60 mg BID or Placebo BID	Number Randomised to GSK2982772 60 mg TID or Placebo TID	Revised Max Total Sample Size	Total + Additional/ Replacement Subjects
7 - 12	24	36	42
12 - 18	24	42	48

The primary objective of the study is safety and tolerability, where there will be 20 subjects randomised to GSK2982772 60 mg TID and up to 12 subjects randomised to GSK2982772 60 mg BID. Using a Bayesian approach to determine the confidence interval (CI) around an observed safety event, we would assume a flat Beta (1, 1) prior, and if we were to observe one safety event in 16 then the posterior distribution would be Beta (2, 16), as outlined below in [Figure 4](#).

**Figure 4 One Event in 16 Subjects: Beta (2,16) Distribution**

Thus, we can be 95% certain that the true probability of the safety event lies between 2% and 25%.

For supportive information, the properties of the key secondary endpoint DAS28 have been considered.

Based on the estimate of variability (SD=1 from historical data) it is estimated that the lower and upper bounds of the 95% CI for the change from baseline in DAS28-CRP score will be within approximately 0.693 and 0.490 of the point estimate of GSK2982772 60 mg TID (n=16) and placebo (n=8).

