### 9.2.2. Sample Size Sensitivity

A sample size sensitivity analysis has been conducted on the primary endpoint to investigate the different safety event rates. If the number of subjects who complete the 12 weeks is higher or lower than 16 in the GSK2982772 group, then the true incidence rates of safety events that could not be ruled out (as outlined in Section 9.2.1) would change. These changes are outlined in Table 5.

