**Table 5 Sample Size Sensitivity**

GSK2982772 subjects completing the study	Number of a particular safety event observed with GSK2982772	Upper limit of exact 95% Credible Interval indicating that a true incidence rate of x% could not be ruled out
20	0	16.1%
20	1	23.8%
20	2	30.4%
18	0	17.6%
18	1	26.0%
18	2	33.1%
16	0	19.5%

GSK2982772 subjects completing the study	Number of a particular safety event observed with GSK2982772	Upper limit of exact 95% Credible Interval indicating that a true incidence rate of x% could not be ruled out
16	1	28.7%
16	2	36.4%
14	0	21.8%
14	1	31.9%
14	2	40.5%
12	0	24.7%
12	1	36.0%
12	2	45.4%

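### Section 9.2.1 labels a 90% credible interval (2% to 25%) as 95%, and Table 5 contradicts it with 28.7% for the same case

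*Protocol*

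**What the plan says.** Protocol Section 9.2.1 says of the sample size that "The study is not powered to detect pre-defined differences". It then describes the precision available for safety, starting from the statement that "The primary objective of the study is safety and tolerability". The method is Bayesian: "we would assume a flat Beta (1, 1) prior". One event among 16 subjects updates this prior to Beta(2,16), and the text below Figure 4 concludes: "Thus, we can be 95% certain that the true probability of the safety event lies between 2% and 25"%.

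Section 9.2.2 carries the calculation to other numbers of completers. It says that, if the number differs from 16, the true incidence rates of "safety events that could not be ruled out (as outlined in Section 9.2.1) would change", and it gives the results in Table 5. The column heading there reads "Upper limit of exact 95% Credible Interval indicating that a true incidence rate of x% could not be ruled out". The row for 16 subjects and one event shows 28.7%.

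**The concern.** The sentence below Figure 4 and the Table 5 row share the same prior, the same data and the same stated credibility level. They should therefore share an upper limit, but one says 25% and the other 28.7%.

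Because the study has no power calculation, these precision figures are the quantitative support for the number of subjects on active treatment. The Section 9.2.1 sentence is the headline example, and its error flatters the design. Table 5 puts the 95% upper limit for one event at 23.8% with 20 subjects and 28.7% with 16. A reader who takes the 16-subject limit from Section 9.2.1 would see almost no loss between 20 and 16 subjects.

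**Working it through.** **Inputs, all from Protocol Section 9.2:** prior Beta(1,1); 1 event in 16; stated 95% interval 2% to 25%; Table 5 entry 28.7% for 16 subjects and 1 event.

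**Posterior.** Beta(1+1, 1+16−1) = Beta(2,16), as the protocol says.

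**Tail formula.** For Beta(2,16), P(p > x) = (1−x)^16 × (1 + 16x).

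**Content of the stated interval.**
- Above 25%: 0.75^16 × 5 = 0.0501.
- Below 2%: 1 − 0.98^16 × 1.32 = 1 − 0.9554 = 0.0446.
- Inside: 1 − 0.0501 − 0.0446 = 0.905.

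**Quantiles of Beta(2,16).**
- 5% and 95%: 2.13% and 25.01%. These round to the printed 2% and 25%, so the plan's figure is reproduced as a 90% equal-tailed interval.
- 2.5% and 97.5%: 1.46% and 28.69%. This is the 95% equal-tailed interval, and its upper limit is the Table 5 entry.

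**Could rounding explain it?** The widest limits that still round to 2% and 25% are 1.5% and 25.5%. They hold 92.8%, which is short of 95%. The narrowest (2.5% to 24.5%) hold 87.9%.

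**Could another 95% method explain it?** None of those tried gives both limits:

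| Method, 1 event in 16 | Lower | Upper |
|---|---|---|
| Highest posterior density, Beta(2,16) | 0.34% | 25.2% |
| Normal approximation to the posterior | −3.0% | 25.2% |
| Jeffreys | 0.68% | 25.7% |
| Wilson | 1.1% | 28.3% |
| Clopper-Pearson | 0.16% | 30.2% |

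**Which of the two places is right?** All 15 entries of Table 5 reproduce to 0.1 point as the 97.5% quantile of Beta(1+x, 1+n−x), where x is the number of events and n the number of subjects. One can be checked by hand: with 0 events in 16 the quantile is 1 − 0.025^(1/17) = 19.5%, as printed. Table 5 is therefore consistently the upper limit of a two-sided 95% equal-tailed interval, and the sentence in Section 9.2.1 is the outlier.

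**Intended convention.** The superseded protocol text used one event in 20, posterior Beta(2,20), and gave 0.01 to 0.24. The 95% equal-tailed interval of Beta(2,20) is 1.2% to 23.8%, which matches. This suggests that the slip came in when the example was recalculated for 16.

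**Size.** 28.7 − 25.0 = 3.7 percentage points on the upper limit. The probability outside the stated interval is 4.5% + 5.0% = 9.5%, against the 5% implied.

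**The case against.** The arithmetic is hard to contest, but four points limit what follows from it.

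- A reader might infer that rates above 25% are not excluded with 95% certainty. That does not follow. P(p > 25%) = 5.0%, so 25.0% is a correct one-sided 95% upper bound. What fails is the two-sided statement that the protocol makes. This point stands.
- Of the 9.5% outside the interval, about 4.5% lies below 2%, where the true rate is lower than stated and safety is not at issue. The excess on the harmful side is about 2.5 points of probability (5.0% against 2.5%). The highest-density 95% interval also ends near 25%, but its lower limit is 0.34%, so it does not rescue the printed pair. The point about the tails stands; the rescue does not.
- It is tempting to call this sentence the sole worked support for the sample size. It is not: Table 5 gives 15 worked cases in the next subsection, including this one with the right limit. That limits how far a reader is misled, but it is also what creates the contradiction.
- The sentence is a hypothetical illustration. The study is not powered, Section 9.1 sets no formal hypothesis for the primary objective, and Section 9.4.1 bases the primary analysis on review and display of safety data. No sample size, stopping rule, interim decision or analysis uses 2% or 25%. This stands, and it sets the severity.

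**Conclusion.** The point holds as a mislabelled interval. Given the protocol's own prior and data, 2% to 25% is the 90% equal-tailed credible interval, with about 90.5% posterior probability. The 95% equal-tailed interval is 1.5% to 28.7%, as Table 5 implies. The headline example overstates two-sided precision, with the upper limit 3.7 percentage points too low.

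The result rests only on the Beta(1,1) prior, one event in 16, and the equal-tailed convention that Table 5 follows throughout. Nothing here shows that the sample size is wrong or that the safety evaluation is compromised, and the documents would not support that reading. Figure 4 is not shown, so whether it carries the same limits is unknown. Severity: should-fix.

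**What to change.** In Section 9.2.1, below Figure 4, do one of two things:
- replace the limits with 1.5% and 28.7%, keeping the 95% label; this matches Table 5 and is the better choice;
- keep 2% to 25% and call it a 90% credible interval, accepting that it then uses a different level from Table 5.

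If Figure 4 marks interval limits, check that they agree with the corrected sentence. Table 5 needs no change. The cost is one sentence at the next amendment and a slightly less favourable printed figure. Sample size, conduct and planned analyses are unaffected.

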### 9.2.2. Sample Size Sensitivity

A sample size sensitivity analysis has been conducted on the primary endpoint to investigate the different safety event rates. If the number of subjects who complete the 12 weeks is higher or lower than 16 in the GSK2982772 group, then the true incidence rates of safety events that could not be ruled out (as outlined in Section 9.2.1) would change. These changes are outlined in Table 5.

**Table 5 Sample Size Sensitivity**

GSK2982772 subjects completing the study	Number of a particular safety event observed with GSK2982772	Upper limit of exact 95% Credible Interval indicating that a true incidence rate of x% could not be ruled out
20	0	16.1%
20	1	23.8%
20	2	30.4%
18	0	17.6%
18	1	26.0%
18	2	33.1%
16	0	19.5%

GSK2982772 subjects completing the study	Number of a particular safety event observed with GSK2982772	Upper limit of exact 95% Credible Interval indicating that a true incidence rate of x% could not be ruled out
16	1	28.7%
16	2	36.4%
14	0	21.8%
14	1	31.9%
14	2	40.5%
12	0	24.7%
12	1	36.0%
12	2	45.4%

### 9.2.3. Sample Size Re-estimation or Adjustment

No sample size re-estimation or adjustment will be conducted.

## 9.3. Data Analysis Considerations

### 9.3.1. Analysis Populations

**All Subjects Population:** The ‘All Subjects Population’ is defined as subjects who were screened for the study. This population is used for the summary of selected accountability data.

**Safety Population:** The ‘Safety Population’ is defined as subjects who receive at least one dose of study medication. This population is used for the summary of all data including demography, safety, efficacy and exploratory data but excluding PK data.

**Pharmacokinetic Population:** The ‘PK Population’ is defined as subjects in the ‘Safety’ population who received an active dose and for whom a GSK2982772 pharmacokinetic sample was obtained and analysed. This population is used for the summary of PK data only. Any PK-PD analysis will be conducted on the Safety population such that subjects receiving placebo can be included.

If 12 or more subjects are randomised to a BID regimen (i.e.,  $\geq 4$  placebo and  $\geq 8$  GSK2982772 60 mg BID) then treatment received will take into account dosing frequency for GSK2982772, otherwise treatment will be irrespective of dosing frequency.

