### **9.4.3. Other Analyses**

In addition, based on the data that we observe in the study, probabilities of success will be determined, where the definition of success will be dependent on the endpoint. For example, what is the probability that we would observe a certain change in DAS28 (i.e., comparator rate), based on the data that we have observed in the study.

GSK2982772 plasma concentrations will be summarised descriptively by day and nominal sampling time.

Further details regarding the statistical analysis will be outlined in the Reporting and Analysis Plan (RAP).

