**Summary of Protocol Amendment Changes with Rationale**

Protocol Amendment 03 incorporates change in dosing regimen from 60 mg BID to 60 mg TID, restrictions on JAK inhibitors, defined non-reproductive potential criteria in Exclusion 11, change to clinical laboratory criteria in Exclusion 23, of evaluation of joint space narrowing with MRI, flexibility in scheduling with MRI and synovial biopsy.

GlaxoSmithKline Document Number of Investigator Brochure GSK2982772 has been updated to 2014N204126\_02 throughout the document. Other minor protocol clarifications and administrative changes are also provided in this amendment.

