**Synopsis and Section 2.1 Study Rationale**

**The primary objective of this study has not changed with amendment 03; however the dosing regimen does change to GSK2982772 (60 mg three times daily for 84 days).**

The primary objective will be to investigate the safety and tolerability of repeat oral doses of GSK2982772 (60 mg ~~twice~~ **three times daily** for 84 days). In addition to the pharmacokinetics (PK), a number of experimental and clinical endpoints will be employed to obtain information on the pharmacodynamics (PD), and preliminary efficacy in subjects with active RA. Although no formal hypothesis will be tested, these endpoints will enable a broader understanding of the mechanism of action and potential for clinical efficacy of GSK2982772 in RA, by making full use of the information obtained from each subject enrolled.

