#### **Section 4.5 Dose Justification**

The **initial** selection of the 60 mg BID dose ~~to be~~ **being** tested in this study is based on the safety, PK, and PD data from the First Time in Human (FTiH) study, 200975. GSK2982772 administered at 60 mg BID for 14 days was well tolerated and no safety concerns were identified. A BID dosing regimen was **initially** selected over a QD dosing regimen due to the short half-life of GSK2982772 in humans (~2h). Based on preliminary PK/PD modelling of ex-vivo RIP1 target engagement and GSK2982772 concentrations from the multiple dose ascending part of Study 200975, a 60 mg BID dose **was** predicted to have on average 95% RIP1 target engagement in blood and approximately 90% of subjects will have >90% target engagement in blood at  $C_{min}$  **using a novel in-house ex-vivo PD/target engagement assay based solely on the TNF pathway which is believed to be a key component of the RIP1 pathway.**

**However, based on final PK/PD modelling from the full repeat dose part of the Study 200975 (up to 120 mg BID), a 60 mg BID dose is now predicted to have on average 99% RIP1 target engagement in blood and approximately 90% of subjects will have >85% target engagement at  $C_{min}$ . This is lower than our target of achieving >90% target engagement in at least 90% of subjects at  $C_{min}$ . Therefore, a 60 mg TID cohort is now being proposed.**

**The  $C_{min}$  values at 60 mg TID are predicted to be approximately 3.5 fold higher than for 60 mg BID. Using the final PK/PD, a 60 mg TID dose is predicted to have on average 99% RIP1 target engagement in blood and approximately 90% of subjects will have > 96% target engagement at  $C_{min}$ .** No data are currently available about the distribution of GSK2892772 into the synovium. Based on data in non-steroidal anti-inflammatory drugs (NSAIDs), the synovial fluid concentrations fluctuate to a much lesser extent than those in plasma [Netter, 1989]. Peak drug concentrations are generally lower in synovial fluid but are similar to plasma at later time points. Assuming the same is true for GSK2982772, a 60 mg ~~BID~~**TID** dose should provide similar RIP1 target engagement at the site of action as predicted in blood.

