## 6.2. Treatment Assignment

At Screening a unique Subject Number will be assigned to any subject who has signed a consent form. The unique Subject Number will be used to identify individual subjects during the course of the study. Any subject that is re-screened outside of the allowed screening window at the approval of the GSK Medical Monitor, must be assigned a new unique Subject Number .

Subjects who meet screening eligibility criteria will be randomised to a treatment group through an Interactive Response Technology System (IRTS). The IRTS will confirm the subject's CRF number (Subject Number) and provide the randomisation number, where:

- A randomisation number will be assigned from a randomisation schedule generated by Clinical Statistics, prior to the start of the study, using validated internal software. Once assigned, this number must not be reassigned to any other subject in the study.

Therefore, the randomisation is centrally controlled by the IRTS.

Subjects will be randomised to receive either GSK2982772 or placebo in a 2:1 ratio.

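### With fewer than 12 subjects on BID, Section 9.3.1 merges BID and TID actives into one GSK2982772 group, so the safety, efficacy and trough results would not describe the TID regimen

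*Protocol*

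**What the plan says.** The grouping rule closes Section 9.3.1 of the protocol, directly after the Safety and PK population definitions. It opens "If 12 or more subjects are randomised to a BID regimen" and continues "then treatment received will take into account dosing frequency for GSK2982772, otherwise treatment will be irrespective of dosing frequency". It is not limited to safety or efficacy, and PK is not exempted. For PK, Section 9.4.3 says only that "GSK2982772 plasma concentrations will be summarised descriptively by day and nominal sampling time"; regimen is not named as a grouping factor.

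On numbers, Section 9.2.1 plans for "approximately 24 subjects with moderate to severe RA are randomised into the study on a TID regimen" and caps BID at 18. Table 4 has one row for 7 to 12 BID subjects and one for 12 to 18. Allocation is 2:1 in both cohorts ("Subjects will be randomised to receive either GSK2982772 or placebo in a 2:1 ratio" in Section 6.2; the Amendment 3 text gives the same ratio for each).

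On intent, Amendment 3 rewrote Section 2.1 to say that the primary objective stands, "however the dosing regimen does change to GSK2982772 (60 mg three times daily for 84 days", and reworded the objectives in Section 3 to three-times-daily dosing. Its text for Section 4.5 gives the reason for the change: BID falls short of the target-engagement goal at Cmin. It adds that Cmin "values at 60 mg TID are predicted to be approximately 3.5 fold higher than for 60 mg BID".

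**The concern.** The TID cohort exists because the sponsor judged BID exposure at trough too low. A rule that merges the two regimens when BID recruitment is small answers a question that the objectives no longer ask. The result labelled GSK2982772 would then be a mixture whose weights depend on how many subjects each country enrolled before it approved Amendment 3. One BID subject more or less, 11 against 12, would change what the primary safety summary and the pre-dose PK summary estimate.

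At stake is interpretation, not error control, since Section 9.1 sets no formal hypothesis for safety. There are two risks. A trough summary could be read as the TID trough. A safety bound could look tighter than the TID data allow because subjects with lower exposure were counted in it.

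**Working it through.** **Inputs.** TID cohort 24 (Section 9.2.1); BID cohort 7 to 12 or 12 to 18 (Table 4); 2:1 allocation (Section 6.2 and Amendment 3); TID/BID Cmin ratio 3.5 (Amendment 3 text for Section 4.5); flat Beta(1,1) prior (Section 9.2.1).

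**The plan's own figures.**
- 12 × 2/3 = 8 active and 12/3 = 4 placebo, the split that Section 9.3.1 states. 24 gives 16 and 8.
- Table 5 is the 97.5% quantile of Beta(1 + x, 1 + n − x). For n = 16 this gives 19.5%, 28.7% and 36.4% for 0, 1 and 2 events. All 15 entries reproduce.
- Section 9.2.1 also says that 20 subjects will be randomised to active TID, which does not fit 24 at 2:1. I use 16 and give the result for 20 below.

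**Below 12 on BID.** Let m be the number of BID actives (2/3 of the BID total, rounded).
- BID share = m/(16 + m).
- Pooled-to-TID trough ratio = (16 + m/3.5)/(16 + m) if 3.5 is a ratio of arithmetic means, or 3.5^(−share) if it is a ratio of geometric means.
- Upper limits come from the Table 5 formula with n = 16 + m.

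| BID randomised | m | Pooled active | BID share | Arithmetic ratio | Geometric ratio | Upper limit, 0 events | Upper limit, 1 event |
|---|---|---|---|---|---|---|---|
| 7 | 5 | 21 | 23.8% | 0.830 | 0.742 | 15.4% | 22.8% |
| 9 | 6 | 22 | 27.3% | 0.805 | 0.711 | 14.8% | 21.9% |
| 11 | 7 | 23 | 30.4% | 0.783 | 0.683 | 14.2% | 21.1% |
| TID alone | – | 16 | 0% | 1 | 1 | 19.5% | 28.7% |

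With 20 TID actives, the share is 5/25 = 20% to 7/27 = 26%, the arithmetic ratio 0.857 to 0.815, and the zero-event limit 13.2% to 12.3% against 16.1% for TID alone.

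**Which PK samples are affected.** The pre-dose samples on Days 8 and 43 and the Day 85 trough fall about 12 h after dosing on BID and about 8 h after dosing on TID. Section 4.5 gives a half-life of about 2 h, so the 4 h gap is two half-lives, roughly 4-fold, in line with the predicted 3.5. Day 1 post-dose samples follow a first 60 mg dose in both regimens, so pooling does little harm there.

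**Event rates.** The pooled rate is (16·pT + m·pB)/(16 + m), so any TID–BID difference shrinks by the BID share. The risks are not in the documents; as assumptions:
- 30% on TID and 10% on BID: pooled 25.2% to 23.9%.
- 20% on TID and 0% on BID: pooled 15.2% to 13.9%.
- Equal risks: no dilution.

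**12 or more on BID.** TID active is its own group of 16. Its event rates, credible limits and concentrations are unaffected.

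**The case against.** The rule is pre-specified, depends on a recruitment count and not on outcomes, and avoids a column of 5 to 7 subjects. The study is descriptive. The Reporting and Analysis Plan is not at hand and may add displays by regimen. Trough is also the measure on which the regimens differ most: Section 4.5 predicts 99% average target engagement for both, total daily dose differs only 1.5-fold (3 × 60 = 180 mg against 2 × 60 = 120 mg), and nothing in the documents ties safety to trough.

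Most of this stands as a limit on size, and it is why no figure for safety dilution can be asserted. It does not rescue the rule. The protocol fixes the grouping itself, so this is a stated choice and not detail left for later. A small BID group is a reason not to draw conclusions about BID, not a reason to count those subjects as TID.

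Three stronger readings are tempting and are not supported.
- *A reader might infer that Section 9.2.1 promises a 16-against-8 comparison that neither branch delivers.* It gives single-arm half-widths, 1.96/√16 = 0.490 and 1.96/√8 = 0.693, as supporting information in a study that is not powered.
- *A reader might infer that placebo is always pooled and therefore confounded with cohort.* Section 9.3.1 limits the split to GSK2982772 and does not say how placebo is shown. If it is pooled with 12 to 18 on BID, 4/12 = 33% to 6/14 = 43% of it comes from the BID cohort, and Amendment 3 did make a "change to clinical laboratory criteria in Exclusion 23". But the switch was made country by country, so the cohorts may overlap in time. Amendment 4 restored the haemoglobin entry limit in Germany. No shift in any endpoint can be derived. It is a point to check, not an established bias.
- *A reader might infer that the MMRM needs a cohort term.* With TID, BID and placebo groups, that term would leave the TID contrast resting on the 8 TID placebo subjects. The standard-error factor would rise from √(1/16 + 1/14) = 0.366 or √(1/16 + 1/12) = 0.382 to √(1/16 + 1/8) = 0.433, which is 18% or 13% wider. That is a trade-off, not a correction.

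**Conclusion.** The concern holds for the branch with fewer than 12 subjects on BID, which Table 4 plans for. There, 24% to 30% of the active group would be on the regimen that TID replaced (20% to 26% if TID actives number 20). The pooled trough would be 78% to 83% of the TID value as an arithmetic mean, or 68% to 74% as a geometric mean. A zero-event upper limit of 14.2% to 15.4% would stand where the TID subjects support 19.5%.

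The shares rest on 2:1 allocation and rounding. The trough figures also rest on the protocol's predicted 3.5-fold ratio, which appears in the Amendment 3 text for Section 4.5. Dilution of event rates is possible but cannot be sized. It should not be read as TID results being diluted whatever the BID count: with 12 or more on BID, TID active stands alone.

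**What to change.** In Section 9.3.1, remove the 12-subject switch for displays. State that safety, efficacy and PK for GSK2982772 are always summarised by regimen, TID and BID, with an any-GSK2982772 column as a supplement. In Section 9.4.3, add regimen to the factors by which plasma concentrations are summarised. Show TID-cohort placebo beside pooled placebo as a descriptive check. A cohort term in the MMRM can remain optional.

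The cost is a wording change in the protocol and the Reporting and Analysis Plan and extra table columns. The BID column may hold only 5 to 7 subjects, and its limits will be wide: one event in 5 gives an upper limit of 64.1%, one in 7 gives 52.7%. It should be presented as descriptive only.
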